POB/ /
Berlaku mulai:

15 Mei 2015

http://www.pjnhk.go.id/

Study Protocol

Hal 1 dari 6

LAMPIRAN 3 FL/03-010/01.0

Study Protocol Summary

Title

Low Dose Continuous Furosemide Effect on Cardiac Surgery Patients With Kidney Dysfunction

Main Researcher

dr. [name], SpAn., M.Kes., KAKV

RS Jantung dan Pembuluh Darah Harapan Kita, Jakarta

Sponsor

none

Aims

- to Analyze trends in estimated glomerular filtration rate parameters from administration of low-dose furosemide continuous infusion in patients with mild-moderate renal dysfunction undergoing cardiac surgery.
- 2. 2. To analyze the need for a therapeutic dose of intravenous diuretic after low-dose continuous furosemide in patients with mild to moderate renal dysfunction undergoing cardiac surgery.
- 3. To analyze the need to use renal replacement therapy as a marker of worsening renal function leading to acute renal failure after continuous administration of low-dose furosemide in patients with renal dysfunction undergoing cardiac surgery.

Ethical Issue(s) of the Protocol

- 1. Administration of fluids or drugs to patients that can affect patient outcomes
- 2. Taking blood samples from patients for laboratory examination
- 3. Evaluating the effects of drug administration
- 4. Patient condition follow up in study period
- 5. Inconvenience of patient or family for additional information needed in research involvement

POB/ /
Berlaku mulai:

15 Mei 2015

Hal 2 dari 6

LAMPIRAN 3 FL/03-010/01.0

http://www.pjnhk.go.id/

Study Protocol

Study Design

Clinical Study: double blinded randomized controlled study

Anticipated Outcome

Perioperative administration of low dose continuous furosemide infusion can gives protective effect in cardiac surgery patients with mild to moderate kidney, Measured by the improvement of post operative eGFR

Inclusion and exclusion criteria

Inclusion criteria:

- 1) 18-65 years old
- 2) Undergo elective heart surgery, types of surgery: coronary bypass (coronary artery bypass graft/CABG), single heart valve replacement surgery, one or two heart valve repair surgery, coronary bypass surgery with single heart valve repair/replacement.
- 3) Using cardiopulmonary bypass machine in surgical procedures
- 4) Patients with ejection fraction >40%
- 5) Patients with mild to moderate impaired renal function (eGFR 30-89 mL/min/1.73 m2 and have never had renal replacement therapy

Exclusion criteria:

- 1) Heart disease patients with ejection fraction < 40%
- 2) Patients with preoperative acute renal failure of any cause
- 3) Patients with stage 4-5 chronic renal failure and/or who require previous renal replacement therapy
- 4) Patients with emergency surgery or undergo redo operation heart surgery
- 5) Patients with complex heart disease, for example those requiring IABP insertion, replacement of more than 2 heart valves, coronary heart disease with severe valve abnormalities, patients with suspected severe pulmonary hypertension.
- 6) Congenital heart disease patients

Study Protocol

POB/ /
Berlaku mulai:

15 Mei 2015

Hal 3 dari 6

LAMPIRAN 3 FL/03-010/01.0

http://www.pjnhk.go.id/

- 7) Patients with major blood vessel (aorta) disorders and/or those affecting the renal artery supply directly
- 8) Patients who are following other studies that affect drug administration
- 9) Patients with hemodynamic compromise caused by bleeding, sepsis, anaphylactic or cardiogenic shock
- 10) Patients who refuse to be involved in the study

Withdrawal or discontinuation Criteria

Kriteria withdrawal:

- Hemodynamically unstable patient (with persistent hypotension, taking > 2 inotropic drugs/ >
 2 vasoactive drugs, patient with IABP, patient with ECMO)
- 2) Patients in cardiogenic shock
- 3) Patients with long use of cardiopulmonary bypass machine (>140 minutes)
- 4) Patients with pulmonary hypertension crisis or severe pulmonary hypertension
- 5) Patients who have to undergo redo surgery for any reasons
- 6) Patients with postoperative bleeding requiring large amounts of transfusion
- 7) Patients given extra bolus furosemide or mannitol outside the established protocol
- 8) Patients with anaphylactic shock of any cause

Interventions

Ethical clearance for the study was approved by Institutional Review Board of National Cardiovascular Center Harapan Kita. Patients eligible for the study was recruited and written informed consent was obtained after clear explanation of the study. Allocation of furosemide and control group was done using simple computer randomization by staff who was not involved in the study. Furosemide infusion and normal saline was prepared by independent pharmacist blinded to the study. Furosemide solution was prepared to contain 40 mg of furosemide diluted with normal saline to a total volume of 40 cc (1 mg / 1 cc) and control solution was prepared to contain only 40 cc of normal saline. Both solution was packaged in 50-cc syringe and prepared in similar fashion. The solution was administered after induction of anesthesia with rate of 2 cc

Study Protocol

POB/ /
Berlaku mulai:

15 Mei 2015

Hal **4** dari **6**

LAMPIRAN 3 FL/03-010/01.0

http://www.pjnhk.go.id/

per hour for 12 hours.

Metode Analisa*

The data obtained will be analyzed using the SPSS software program. Basic characteristic data will be displayed according to the specified variable type. Numerical variables with normal distribution will be displayed in the form of mean ± standard deviation or median (minimum-maximum) if the distribution is not normal. Categorical variables will be displayed as a percentage (amount). Data from the two groups were analyzed using x2 analysis (chi square) or Fisher's exact test, respectively. The level of statistical significance refers to the P value <0.05

Evaluation Criteria (Response/Outcome)

changes in glomerular filtration rate parameters after intervention in subjects will be evaluated, the need/indication for therapeutic diuretic therapy, and use of renal replacement therapy, length of stay in the ICU and incidence of mortality will be analyzed.

Safety Parameters Criteria (Toxicity)

Renal Function pre and post treatment

Blood gas analysis

Blood electrolyte

POB/ /
Berlaku mulai:

15 Mei 2015

Study Protocol Hal 5 dari 6

LAMPIRAN 3 FL/03-010/01.0

http://www.pjnhk.go.id/

Abstract

[figure not shown]
Background:

Renal dysfunction is consistently an independent risk factor for the development of cardiovascular disease. Several studies have identified that renal dysfunction increases the risk of mortality in patients undergoing cardiac surgery and that the risk increases with the degree of renal dysfunction. Several strategies are used to prevent worsening of kidney function, such as the use of loop diuretics furosemide as prophylactic. Several recent studies have investigated the protective effect of furosemide in cardiac surgery in preventing worsening of renal function, but these studies mostly were conducted in patients with normal renal function. Patients with preoperative renal dysfunction are more in urgent need of effective renal protective strategies. Based on above, this study aimed to analyze the effect of continuous administration of low-dose furosemide on patients with mild to moderate renal dysfunction undergoing cardiac surgery.

Methods:

The study design was a double-blind randomized controlled trial. Subjects will be randomly divided into 2 groups; the furosemide group (n=43) and the control group (n=44). This study started since May 28, 2021; after obtaining an ethical clearance from the hospital ethics committee. Inclusion criteria included patients aged 18-65 years with left heart ejection fraction >40%, mild to moderate renal dysfunction category (eGFR 30-89 mL/min/1.73 m2) who underwent elective cardiac surgery; such as coronary artery bypass graft (CABG), replacement of one heart valve, repair of one or two heart valves, and using cardiopulmonary bypass machine. Exclusion criteria included heart disease patients with stage 4-5 chronic renal failure, on renal replacement therapy, cardiac ejection fraction <40%, emergency or repeat surgery, complex heart disease, congenital heart disease, aortic vascular surgery, massive bleeding, sepsis, and currently participating in other research. Continuous furosemide (2 mg/hour) or 0.9% NaCl (2 mL/hour) was given after the induction of anesthesia and continued until 12 hours of administration. After drug administration was completed (12 hours) the first blood sample was obtained to check blood urea nitrogen concentration, urea, creatinine serum and estimated glomerular filtration rate. Sampling was repeated again at the 24th hour, 48th hour and 120th hour since the drug was started. A decrease in GFR > 20% of the preoperative value is considered a decrease in renal function, and an increase of >20% of third sample value in the fourth sample is considered an improvement of renal function. Deterioration of renal function to severe renal dysfunction or requiring renal replacement therapy is considered an event of acute renal failure.

Keywords: Furosemide, Glomerulus Filtration Rate, Renal Dysfunction, Cardiac Surgery

Researcher,

dr. [name], SpAn, M.Kes, KAKV

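### Four of the eight withdrawal criteria can be met only after study drug starts, and the plan neither separates stopping drug from leaving the study nor names an analysis set

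*Combined protocol and SAP*

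**What the plan says.** The section Withdrawal or discontinuation Criteria has one list of eight items under the single subheading "Kriteria withdrawal". It includes "Patients with long use of cardiopulmonary bypass machine (>140 minutes", "Patients who have to undergo redo surgery for any reasons", "Patients with postoperative bleeding requiring large amounts of transfusion" and "Patients given extra bolus furosemide or mannitol outside the established protocol". The remaining items are haemodynamic instability (including IABP, ECMO or more than two inotropic or vasoactive drugs), cardiogenic shock, pulmonary hypertension, and anaphylactic shock.

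Under Interventions and in the Abstract, study drug starts after induction of anaesthesia and runs for 12 hours. The Abstract schedules blood samples at the end of the infusion and at 24, 48 and 120 hours from drug start. Evaluation Criteria lists change in GFR, need for therapeutic diuretics, renal replacement therapy (RRT), ICU stay and mortality.

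Metode Analisa says that the two groups are compared by chi-square or Fisher's exact test. It does not say which patients make up the groups, or how withdrawn patients or missing samples are handled. Ethical Issue(s) of the Protocol mentions following patients' condition during the study, but does not say that this covers withdrawn patients.

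**The concern.** A patient who bleeds heavily, returns to theatre or has a long bypass run has been randomised and has started study drug. The plan does not say whether such a patient only stops the infusion, also stops being sampled, or drops out of the comparison. Under the last two readings, the outcomes are assessed in patients selected by what happened after allocation. The result would then describe uncomplicated cases and not everyone randomised, and outcomes in the removed patients could go unrecorded. Because the analysed set determines every listed outcome, the choice should be made before unblinding.

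**Working it through.** **Timing of each criterion against the start of infusion**

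The time of randomisation relative to induction is not stated. The syringe must be allocated and prepared before the infusion, however, so anything after drug start is after randomisation.

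| Criterion | When it can be met |
|---|---|
| 1 Instability, IABP, ECMO, multiple inotropes or vasoactives | Before or after |
| 2 Cardiogenic shock | Before or after |
| 3 Bypass over 140 minutes | Only after |
| 4 Pulmonary hypertension | Before or after |
| 5 Redo surgery (redo operations at entry are excluded, so read as re-operation) | Only after |
| 6 Postoperative bleeding with large transfusion | Only after |
| 7 Extra furosemide or mannitol bolus | Only after, in practice |
| 8 Anaphylactic shock | Before or after |

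Four of eight are met only after the start. Criteria 5 and 6 can also occur after the 12-hour infusion has ended, when there is no drug left to stop. That makes leaving the study a plausible meaning of the list, but does not establish it.

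**How much could be left unknown**

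No withdrawal rate or event rate is given, so only a worst-case limit can be computed. The inputs are 43 and 44 (Abstract, taken as randomised counts) and assumed numbers *a* and *b* of withdrawn patients whose binary outcome is not recorded. Each such outcome could be 0 or 1, so the all-randomised risk difference lies in an interval of width *a*/43 + *b*/44.

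- One patient: 1/43 = 2.33 points, or 1/44 = 2.27 points
- 4 and 4: 9.30 + 9.09 = 18.4 points
- 6 and 7: 13.95 + 15.91 = 29.9 points
- 9 and 9: 20.93 + 20.45 = 41.4 points

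For scale, the sampling standard error of the risk difference is √[p(1−p)(1/43 + 1/44)], which is 6.4 points at p = 0.10 and 10.7 points at p = 0.50. The widths are limits and not estimates of bias.

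**When the arms would be biased against each other**

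Let p be an arm's full risk, w the share withdrawn and q the risk among those withdrawn. The risk in those retained is (p − wq)/(1 − w). Assume a drug with no effect on the outcome and p = 0.30 in both arms.

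- 10% withdrawn in each arm, q = 0.60: (0.30 − 0.06)/0.90 = 26.7% in both. The gap is 0, but the risk is understated.
- 10% v 20% withdrawn, q = 0.30: 30% in both, gap 0.
- 10% v 20% withdrawn, q = 0.60: 26.7% v (0.30 − 0.12)/0.80 = 22.5%, gap 4.2 points.
- 10% v 20% withdrawn, q = 0.80: (0.30 − 0.08)/0.90 = 24.4% v (0.30 − 0.16)/0.80 = 17.5%, gap 6.9 points.

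Swapping the arms reverses the sign. In these illustrations a systematic gap appears only when withdrawal differs by arm and is related to risk. All these rates are assumed, so the documents fix neither size nor direction.

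**The case against.** The heading also contains the word discontinuation, so the list may be only a rule for stopping the infusion. The document is a summary, in which silence carries less weight than in a full SAP. The trial is double-blind, so knowledge of the arm should not drive withdrawal. All of this stands: between-arm bias would need the drug itself to affect a withdrawal trigger, which is possible but not shown. Blinding does not, however, restore outcomes that were not recorded, and nothing in the documents rules out removal.

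Three stronger readings are tempting.

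- **Withdrawn patients will be left out of the analysis.** A reader might infer this from the overlap with the exclusion list, which has "Patients with hemodynamic compromise caused by bleeding, sepsis, anaphylactic or cardiogenic shock" and "Patients with complex heart disease, for example those requiring IABP insertion, replacement of more than 2 heart valves", and from the Abstract, which lists "aortic vascular surgery, massive bleeding, sepsis, and currently participating in other research" among its exclusions, as if eligibility were re-applied after allocation. The overlap does not discriminate, because a rule for stopping study drug would name the same serious conditions. The Abstract's bleeding item is plausibly a short form of the exclusion for haemodynamic compromise.
- **Most criteria arise only after drug start.** The count is four of eight. The exclusions make it likely that the other four mainly catch later events, but those four are not confined to that period.
- **Criterion 7 deletes the diuretic-need outcome (aim 2).** It covers only boluses outside an established protocol, and these documents do not describe that protocol for diuretics. Overlap is possible and not established.

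**Conclusion.** The point holds as a gap in the plan with a definite consequence under one plausible reading. Half of the withdrawal criteria describe events after allocation, drug stopping is not distinguished from leaving the study, and no analysis set is named. If the list is applied as study withdrawal, eGFR, diuretic need, RRT, ICU stay and mortality are compared in a set selected on complications after randomisation. The documents do not say that this will be done, and no bias has been demonstrated.

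The size is a limit of about 2.3 points of an arm's risk per unrecorded outcome. It rests on 43 and 44 being randomised counts; the withdrawal numbers are assumed. It applies mainly to the eGFR outcomes, because RRT, ICU stay and death are assumed to be recoverable from hospital records. No figure is offered for ICU stay.

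**What to change.** - State that meeting any of criteria 1 to 8 does not end outcome follow-up. Define stopping study drug separately from leaving the study.
- Follow all randomised patients for eGFR to 120 hours and for diuretic need, RRT, ICU stay and death.
- Make analysis of all randomised patients in their assigned arm primary. Keep the set without withdrawn patients as a sensitivity analysis.
- Report withdrawals by arm and reason, with analysed counts beside the numbers randomised.
- State before unblinding how eGFR after RRT or death is handled.
- Describe the established protocol to which criterion 7 refers, and reconcile criterion 7 with aim 2 and the diuretic-need outcome, so that a patient counted as needing a diuretic is not removed for receiving one.

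No dose or clinical stopping rule is changed. The cost is mainly protocol and SAP wording. The later samples are timed from drug start and stay defined if the infusion stops early; the first is tied to completing the infusion and needs a stated time for such patients. The downside is more variable eGFR data and some missing samples. The study began on May 28, 2021, so any samples already missed in withdrawn patients cannot be recovered.

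### Withdrawal item 7 can take out randomised patients for an extra diuretic bolus that may itself be an Aim 2 event, and nothing keeps withdrawn patients in follow-up or analysis

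*Combined protocol and SAP*

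**What the plan says.** Under the heading "Withdrawal or discontinuation Criteria", the protocol summary lists eight items. Item 7 is "Patients given extra bolus furosemide or mannitol outside the established protocol". The list's own label uses only the word withdrawal.

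Aim 2 is "To analyze the need for a therapeutic dose of intravenous diuretic after low-dose continuous furosemide" in patients with mild to moderate renal dysfunction. The Evaluation Criteria section repeats this as an outcome: "the need/indication for therapeutic diuretic therapy, and use of renal replacement therapy". The Anticipated Outcome section says that the protective effect is to be "Measured by the improvement of post operative eGFR".

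The only diuretic regimen described is the study infusion: 2 mg/h of furosemide, or saline at the same rate, for 12 hours from induction of anaesthesia. The first blood sample follows at 12 h. After that, "Sampling was repeated again at the 24th hour, 48th hour and 120th hour since the drug was started". Improvement of renal function is defined by the fourth sample against the third.

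On analysis, the Metode Analisa section says: "Data from the two groups were analyzed using x2 analysis (chi square) or Fisher's exact test, respectively". It names no analysis set and has no rule for missing data.

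**The concern.** A furosemide bolus is an intravenous diuretic dose. One clinical act can therefore meet the wording of item 7 and also be what Aim 2 sets out to count. If the patient then leaves the study, the diuretic outcome loses an event, and that patient's later eGFR samples may be lost too. A patient withdrawn before 120 h and not sampled further cannot be classified for improvement. One withdrawn before 12 h has no postoperative sample at all.

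The trigger occurs after randomisation, and because the study drug is itself a diuretic, treatment may change how often it occurs. Selecting patients on such an event can undo the comparability that randomisation gives. The lack of a follow-up and analysis rule affects all eight items. Item 7 stands out because its trigger may itself be a study outcome.

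**Working it through.** **1. Do the documents separate an item 7 bolus from an Aim 2 event?** Two separations are possible.

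- *Inside or outside the protocol.* Item 7 covers only boluses outside it, which implies that some diuretic use is inside it. The summary gives no rescue drug, dose, trigger or window and cites no local procedure, so the boundary is undefined.
- *During or after the infusion.* Aim 2 uses the word 'after', so boluses in the first 12 h could be withdrawals and later ones outcomes. Item 7 has no time window, so a bolus at 30 h could still fall under both.

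**2. Do withdrawn patients stay in the data?** The section heading also mentions discontinuation, which could mean stopping study drug only. After 12 h, however, no infusion is left to stop, so that reading leaves item 7 with nothing to do for later boluses. No sentence says that withdrawn patients are still sampled or are analysed in their group.

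**3. Size of the effect within one arm.** The plan states no event rate, withdrawal count or power, so there is no figure to reproduce. The inputs are 43 furosemide and 44 control patients (Abstract, Methods), taken here as the numbers randomised. Suppose an arm of n patients loses d event patients and keeps e events. The observed rate is p = e/(n − d), and the understatement is

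(e + d)/n − e/(n − d) = (d/n) × (1 − p).

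This is exact.

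- One patient: 1/44 = 2.27 points or 1/43 = 2.33 points, times (1 − p). The ceiling is 2.3 points. At p = 50% in the control arm it is 2.27 × 0.5 = 1.14 points. At p = 10% in the furosemide arm it is 2.33 × 0.9 = 2.09 points.
- Five patients: five times these, 5.7 to 10.5 points.

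**4. Direction between arms (all rates and losses assumed).**

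- *Equal loss.* With true rates of 20% (furosemide) and 40% (control) and half of event patients lost in each arm, the observed rates are 0.10/0.90 = 11.1% and 0.20/0.80 = 25.0%. The odds ratio stays at 0.375. The difference falls from 20 to 13.9 points, and power from 53% to about 35% (two-sided 0.05).
- *Unequal loss with no true effect, 40% in both arms.* Losing 50% of control and 25% of furosemide event patients gives 8.8/35.2 = 25.0% in control and 12.9/38.7 = 33.3% in furosemide, an odds ratio of 1.5 (furosemide against control). The reverse pattern gives 33.3% in control and 25.0% in furosemide, 0.667. The bias can go either way.
- *Small losses.* With 18 events per arm, losing five from furosemide gives P = 0.53 and losing five from control gives P = 0.43. Uncorrected chi-square reaches P<0.05 only after 12 are lost from one arm. Fisher's exact test still gives P = 0.078 after 12 are lost from furosemide.

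**The case against.** The best defence is that item 7 is an ordinary rule against off-protocol co-treatment. It covers extra boluses outside the protocol, whereas Aim 2 counts a therapeutic dose needed after the infusion, and the outcome is worded as need or indication. The document is also a summary, so a rescue-diuretic rule may exist elsewhere. This much stands: the overlap is possible, not shown.

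A reader might infer that the trial is bound to delete its own outcome events. The documents do not support that. It requires item 7 boluses to be Aim 2 events, and it requires withdrawal to mean leaving the data. Neither is settled.

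A reader might also infer that the loss favours one arm. The trial is double-blind with similarly prepared syringes, so boluses should be ordered without knowledge of allocation, which limits differential withdrawal driven by clinicians. Blinding does not remove differences caused by the drug itself, but nothing in the documents fixes their sign.

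The defence does not supply what is missing: a definition of in-protocol diuretic use, a time window for item 7, or a sentence that keeps withdrawn patients in follow-up and analysis.

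**Conclusion.** The point holds as an undefined boundary combined with a missing follow-up and analysis rule, and it should be fixed. Applied on its natural reading, the text drops randomised patients for an event that treatment can affect and that may be an outcome. The only firm size is the within-arm identity, at most 2.3 points per event patient removed, given 43 and 44 randomised. The scenario figures rest on assumed rates and show only that bias could run in either direction; small losses mainly shift estimates rather than produce false significance. If withdrawal means stopping study drug only and everyone is analysed, the harm does not arise, and the text should say so. Confidence is medium, because the diuretic rules that item 7 refers to are not in the summary.

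**What to change.** - Make item 7 and the other seven items reasons to stop study drug only.
- Continue the remaining 12, 24, 48 and 120 h samples, and analyse all randomised patients in their assigned group.
- Record every non-study intravenous diuretic from the drug chart: drug, dose, time and indication.
- Count an indicated therapeutic intravenous diuretic given after the infusion as the Aim 2 event, which keeps the protocol's own window. Report use from the start of study drug to 120 h alongside it. The second count matters because early doses can differ by arm. In an assumed example with 40% use in both arms, where 50% of control and 25% of furosemide users are dosed only in the first 12 h, the later window alone shows 8.8/44 = 20.0% against 12.9/43 = 30.0%.
- If a rescue-diuretic rule exists, cite it and state its trigger and dose.

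The cost is a few sentences and one case-report-form line. The eGFR comparison then includes the effect of rescue diuretic and may be slightly diluted. Need has to be judged from the recorded indication. The study started on May 28, 2021, so samples already missed cannot be recovered, although diuretic doses can still be read from the chart.

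### Neither allocation nor analysis uses baseline eGFR, although entry spans 30-89 and the acute renal failure event is partly an absolute level that depends on it

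*Combined protocol and SAP*

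**What the plan says.** **Entry.** Inclusion criterion 5 admits "Patients with mild to moderate impaired renal function (eGFR 30-89 mL/min/1.73 m2 and have never had renal replacement therapy". Mild and moderate dysfunction are pooled, and every patient has an eGFR value before entry.

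**Allocation.** Interventions: "Allocation of furosemide and control group was done using simple computer randomization by staff who was not involved in the study". No stratification, blocking or minimisation is mentioned. The Abstract (Methods) gives arms of 43 (furosemide) and 44 (control).

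**Analysis.** The Metode Analisa section names chi-square or Fisher's exact test for comparing the groups, at P <0.05. It names no covariate, no stratified comparison and no model for eGFR as a continuous measure.

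**Outcomes.** The Abstract (Methods) scales one renal outcome to the patient: "A decrease in GFR > 20% of the preoperative value is considered a decrease in renal function". It defines another by an absolute level or by treatment: "Deterioration of renal function to severe renal dysfunction or requiring renal replacement therapy is considered an event of acute renal failure". Evaluation Criteria adds change in GFR, diuretic need, renal replacement therapy, ICU stay and mortality.

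**Prognosis.** The Abstract (Background) reports that "renal dysfunction increases the risk of mortality in patients undergoing cardiac surgery and that the risk increases with the degree of renal dysfunction".

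**The concern.** Baseline renal function is the variable that defines this population. The plan itself treats its degree as prognostic for mortality, which is one of the outcomes to be analysed. The absolute part of the acute renal failure definition ties that event directly to entry eGFR: the closer a patient starts to the severe range, the smaller the fall that counts as an event.

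In a trial of 87 with unrestricted allocation, the arms may differ by chance in their share of moderate patients. If they do, the named tests have no means of correcting for it, and readers would be left to judge how much of an observed difference reflects case mix. Even when the arms are balanced, ignoring a strong predictor of post-operative eGFR wastes information that a small trial needs.

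**Working it through.** **Inputs from the documents.** Arms of 43 and 44 (sum 87); entry eGFR 30-89 (89/30 = 2.97-fold); simple randomisation; unadjusted chi-square or Fisher's exact test. The plan states no imbalance probability, power or event rate, so it has no figure of its own to reproduce.

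**Assumptions.** The share p of patients with moderate dysfunction is 20-50%. Moderate means eGFR 30-59 and mild 60-89. Severe means eGFR below 30, inferred from the entry floor and the exclusion of stage 4-5 disease. The documents give none of these.

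**1. Fall needed to reach the severe threshold.** (b - 30)/b for baseline b:

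| Baseline eGFR | Fall to 30 |
|---|---|
| 35 | 14% |
| 40 | 25% |
| 60 | 50% |
| 89 | 66% |

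**2. Chance imbalance in the moderate share.** SE = sqrt[p(1 - p)(1/43 + 1/44)], with 1/43 + 1/44 = 0.0460. The probabilities are exact, from independent Bin(43, p) and Bin(44, p):

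| p | SE (points) | P(difference ≥10 points) | P(difference ≥15 points) |
|---|---|---|---|
| 0.2 | 8.6 | 0.23 | 0.08 |
| 0.3 | 9.8 | 0.30 | 0.13 |
| 0.4 | 10.5 | 0.37 | 0.15 |
| 0.5 | 10.7 | 0.39 | 0.16 |

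A difference of at least 5 points has probability 57-67%, and one of at least 20 points 2-5%. Two other ways of modelling the allocation agree closely. Fixing the number of moderate patients and the arm sizes (hypergeometric) gives 24-39% and 10-19% for 10 and 15 points. Tossing a fair coin for each of 87 patients gives 26-39% and 8-17%.

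**3. The same question on the eGFR scale.** SE of the difference in means = SD × sqrt(1/43 + 1/44). For an assumed SD of 12 to 17 (17 corresponds to a uniform spread over 30-89), the SE is 2.6-3.7. A baseline difference of at least 5 mL/min/1.73 m2 then has probability 5-17%.

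**4. What an imbalance does to a binary comparison.** Shift = imbalance × risk gap between categories. With an assumed gap of 20 points:
- a 10-point imbalance shifts the comparison by 0.10 × 20 = 2 points, or 0.02 × 43 = 0.9 patients;
- a 20-point imbalance shifts it by 0.20 × 20 = 4 points, or 0.04 × 43 = 1.7 patients.

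**5. Effect on the error rate.** Trials were simulated with no drug effect, moderate/mild risks of 25%/5% or 30%/10%, and p of 0.3 or 0.5. Unadjusted chi-square rejects in 4.9-5.2% of all trials, and in about 6-7% of those with an imbalance of at least 10 points. In the latter, the mean absolute shift is about 3 points, against a sampling SE of 6.7-8.6 points.

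**6. What stratified allocation would achieve.** With blocks of 4 in two strata, the arms differ by at most 2 patients per stratum, so the moderate share can differ by at most about 3-4 points for p from 0.2 to 0.5.

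**The case against.** Simple randomisation is a valid method, and stratifying is a choice made for efficiency. Type of surgery also varies in this trial and could claim the same treatment. These points stand. The case for eGFR rests on its link to an outcome definition and on its already being collected.

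A reader might infer three stronger conclusions, none of which the documents support.

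- *A sizeable imbalance is likely.* In every scenario a difference of 10 points or more has a chance below 50%, and one of 20 points or more about 2-6%. Only a small difference, of 5 points or more, is more likely than not.
- *Baseline category largely decides the renal outcomes.* The Background sentence concerns mortality. Nothing in the documents links category to diuretic need or to renal replacement therapy. The 20% decline is scaled to the patient's own preoperative value, and improvement is judged against the third sample. That reduces dependence on baseline, though it does not remove it. Only the severe-dysfunction part of acute renal failure is an absolute eGFR level, and Evaluation Criteria does not list acute renal failure as an outcome in its own right.
- *The comparison is biased, or would mistake imbalance for drug effect.* Chance imbalance is already within the test's overall error rate, as step 5 shows.

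A further objection is that it may be too late to change allocation. Interventions describes it as done, and the Abstract dates the start to May 2021, although the same Abstract puts the division into groups in the future tense. The documents do not settle whether any allocation remains, so the analysis must carry the main remedy.

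The 43/44 split itself is no evidence of trouble: so near-even a split has a 17% chance under simple randomisation.

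**Conclusion.** The point holds as a gap in precision and credibility, not as a threat to validity. The plan has baseline eGFR for every patient and uses it at neither stage. The chance of a 10-point imbalance is roughly one in four to two in five, given the assumed moderate share and cut at 60. The likely distortion of a binary result is modest: one or two patients in an arm, if the risk gap between categories is 20 points. That is still worth removing in a trial of 87. The absolute acute renal failure criterion is where dependence on baseline is clearest. The conclusion that baseline eGFR goes unused does not depend on the assumed share; only the probabilities do.

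**What to change.** Before unblinding, add to the analysis section:

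1. **Post-operative eGFR:** compare the groups with baseline eGFR as a continuous covariate, by ANCOVA at a named time point or by a repeated-measures model over 12, 24, 48 and 120 hours. This serves Aim 1, which a stratified test for binary data does not, and it avoids discarding information by cutting eGFR into two categories.
2. **Binary renal outcomes** (20% decline, acute renal failure, renal replacement therapy, diuretic need): compare stratified by baseline eGFR category with Mantel-Haenszel, or with an exact stratified test if events are few. State the category boundary in advance; 30-59 versus 60-89 is a suggestion, since the documents give none.
3. **If any allocation remains:** use permuted blocks of varying size, stratified by screening eGFR category and still run by the independent staff, and keep the stratum in the analysis. If allocation is complete, items 1 and 2 are the whole remedy.

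Cost: slightly more analysis work and, for item 3, two allocation lists and telling the allocating staff the eGFR category. No extra patients, visits or blood tests are needed.
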